5.2.3 Hypotheses to be accepted or rejected by statistical data from the study

The primary hypothesis is that the time period from index therapy to release for oral food intake (in upper GI tract use) or endoscopic release for stoma relocation (in lower GI tract use) will be superior to historic controls from literature reporting standard management of therapy without use of EVAC therapies.

A Statistical Analysis Plan (SAP) will be prepared prior to start of data analysis detailing the statistical analysis methods which will be used.

5.3 Scientific justification and clinical relevance for effect sizes, non-inferiority margins or equivalence limits

This observational study will provide information on "real world" use and practice in treatment of both upper and lower GI tract perforations and anastomotic insufficiencies using the Suprasorb[®] CNP endo system in a routine clinical care setting.

The indication for this treatment is decided in acute clinical situations needing urgent treatment, thus, a controlled clinical trial setting will be impractical and may lead to a larger selection bias compared to a study which reports observation of routine clinical care without pre-defined study procedures and interventions.

The study will only be performed in study sites which are trained for the use of the Suprasorb[®] CNP endo system treatment in routine clinical care and generally experienced in use of EVT for treatment of upper or

lower GI tract perforations and anastomotic insufficiencies. Thus, comparability in selection of patients, decision on indication and procedures performed can be presumed.

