6.3 Subjects

About 110 adult female and male patients with acute defects, injuries and wounds in the oesophagus or rectum and an indication of treatment with Suprasorb[®] CNP endo system according to IFU and medical guidelines will be enrolled. Patients' written informed consent to use their routine clinical data according to data privacy standards must be obtained prior to documentation of patients' data in the e-CRF. All patients in whom the device has been used will be followed during routine clinical practice and will visit a site only in the course of their routine clinical care. No additional treatment or medical examinations will be performed.

It will be assured by means of the e-CRF system that treatments of upper GI tract and lower GI tract will be about equally balanced over the total study population.

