6.3.6 Expected duration of each subject's participation

The mean follow-up period (from date of enrolment to end of follow-up) of all patients is expected to be about 3 months.

6.3.7 Number of subjects required to be included in the study

As discussed in 3.2, the evidence for the different treatment options is very limited. Especially the patient populations, e.g. regarding underlying diseases, as well as the processes in the therapy are very different in the individual studies published. Therefore a reasonable sample size calculation is not possible at the moment. Thus, an interim analysis with sample size re-calculation is planned.

The best evidence for an **initial sample size calculation** is provided by data of the study by Wasmann et al. [29], a cohort study including 334 patients with ileal defects, where EVAC therapy was compared to conventional management of defect treatment. The median time to stoma relocation was estimated as 4 months in the EVAC group (interquartile range 3 to 6 months) versus 4 months (3 to 13 months) in the conventional management group. Therefore, the proportion of patients with stoma relocation after 6 months is known as 75% in the EVAC group. Assuming a constant increasing proportion in the conventional management group from 4 to 13 months with 2.8% per month, a proportion of 56% stoma relocations after 6 months is expected for the conventional group. Even if the follow-up is set to 3 months in this study, sample size calculation can be based on 6 months results.

Sample size calculation was performed with PASS 16.0.3 using a two-sided, one-sample log rank test. A group sequential design with the alpha spending function of O'Brien-Fleming results in a two-sided type one error of 4.92% for the final analysis. A sample size of 99 analysable subjects achieves 80% power to detect shorter time to release for food intake or endoscopic release for stoma relocation (assuming a proportion of relocated stoma of 75% after 6 months in the EVAC group when the proportion in the historic control group is 56%). The expected number of events during the study with 3 months of follow-up is 13. It is assumed that the survival time distributions of both groups are approximated reasonable well by the Weibull distribution with a shape parameter of 1.00. To account for treatment switching and early drop-outs of 10%, 110 analysable patients will be enrolled.

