6.5 Monitoring plan

No routine onsite monitoring is initially planned within this non-interventional, observational study. Since only observation of routine clinical care without any protocol-defined interventions will be performed, the safety and well-being of study patients is the scope of routine clinical care. Thus, onsite monitoring could be justified for double-check of completeness and quality of data, only. Data quality will primarily be controlled by means of statistical checks on data available for all study sites allowing to detect outliers, extremes and deviation in distribution of data. In case of suspicious findings, on-site visits in corresponding sites might be performed.

7. Statistical considerations

In this observational study the time period from index therapy to release for oral food intake (in upper GI tract use) or endoscopic release for stoma relocation (in lower GI tract use) will be compared to published historic controls. For this, the time period is compared to published data of other EVAC and conventionally managed therapy, especially data from Wasmann et al. [29]. In addition, after half of the patients with complete follow-up, an interim analysis will be performed and sample size will be recalculated. It is expected that until then the results of a randomized clinical trial comparing an EVAC therapy to standard minimally invasive oesophagectomy (refer to NCT04162860 and [22]) will be available for adaptation of assumed confidence intervals and sample size (see 6.3.7). The hypothesis of superiority against conventionally managed therapy will be tested confirmatory.

For primary analysis a one-sample log-rank test will be used, comparing the observed number of events to the expected number of events of the control groups. The two-sided type-one error is 0.54% for the interim analysis and 4.92% for the final analysis.

Data from all study sites will be pooled for analysis. Standard statistical methods will be used to analyse all data. Continuous variables will be summarized using the number of observations, mean, median, standard deviation, minimum and maximum values. Categorical variables will be summarized using the number of observations and percentages.

A separate Statistical Analysis Plan will be prepared prior to the start of data analysis, detailing the statistical analyses methods that will be used.

8. Data management

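### The stated 80% power covers oral-intake release and stoma release together, but only stoma-relocation rates were entered, and no conventional oral-intake reference is named for the single confirmatory test

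*Protocol*

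**What the plan says.** Section 6.1.3.1 defines the primary endpoint by two events: release for oral food intake in upper-GI use, and endoscopic release for stoma relocation in lower-GI use. Lower-GI patients without a stoma are also judged on oral intake. Section 6.3 says that "treatments of upper GI tract and lower GI tract will be about equally balanced over the total study population".

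Section 6.3.7 takes its rates from one cohort of 334 patients with ileal defects and the outcome time to stoma relocation. The vacuum-therapy rate at 6 months is 75%, and "a proportion of 56% stoma relocations after 6 months is expected for the conventional group". The section then says that 99 analysable subjects give a design that "achieves 80% power to detect shorter time to release for food intake or endoscopic release for stoma relocation (assuming a proportion of relocated stoma" at those two rates). It adds: "The expected number of events during the study with 3 months of follow-up is 13".

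Section 5.2.3 sets one primary hypothesis for both events, that the time "will be superior to historic controls from literature reporting standard management of therapy without use of EVAC therapies". Section 7 implements it: "a one-sample log-rank test will be used, comparing the observed number of events to the expected number of events of the control groups". Section 7 also states: "The hypothesis of superiority against conventionally managed therapy will be tested confirmatory". The stoma cohort is the only published source singled out there for the comparison.

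**The concern.** In a one-sample log-rank test the reference curve is the null hypothesis. Patients whose event has no reference curve have no null hypothesis, and without an assumed effect they contribute no known power. Section 6.3.7 nevertheless attaches 80% power to both events.

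The upper-GI comparisons in section 3.2 report closure, strictures, mortality, therapy duration and hospital stay. The colorectal comparison reports closure time, hospital stay and costs. None gives a conventional-care time to oral intake. The randomised oesophagectomy trial mentioned in sections 6.3.7 and 7 is cited for updating assumptions and sample size. No oral-intake rate is given from it, and it is not named as the reference for the test.

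At stake is whether a confirmatory superiority result, or a failure to reach one, can be read against the power the protocol prints.

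**Working it through.** **Share of patients judged on oral intake.** Upper GI is about 50% (section 6.3). Section 3.2 gives a diversion rate of 76.4% (95% CI 64.9-85.0%) in colorectal patients treated with vacuum therapy. If it applied here, the share would be 0.50 + 0.50 × (1 − 0.764) = 61.8%, with a range of 57.5% (at 85.0%) to 67.6% (at 64.9%). Of 99 patients, the split between oral intake and stoma is then 50/49 if every lower-GI patient has a stoma, or 61/38 at 76.4% diverted (49.5 × 0.764 = 37.8).

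**The plan's own figure.** Inputs: exponential times (Weibull shape 1.00), 3 months of follow-up, two-sided alpha 4.92% (z = 1.967), power 80% (z = 0.842). The 56% follows from 50% at 4 months plus 2 × 2.8% = 55.6%. The formula is

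n = (1.967·√p0 + 0.842·σ1)² / (p1 − p0)²

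where p1 is the event probability within 3 months, p0 the expected cumulative hazard under the reference, and σ1 the standard deviation of O − E per patient under the alternative.

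- Coding that reproduces the plan (56% and 75% entered as patients still without the event): hazards −ln(0.56)/6 = 0.0966 and −ln(0.75)/6 = 0.0479 per month; p1 = 0.1340, p0 = 0.2700, σ1 = 0.3924. n = (1.022 + 0.330)² / 0.1360² = 98.8, so 99. Power is 80.1%, events are 99 × 0.1340 = 13.3, and 99/0.9 = 110.
- Coding as the text words it (56% and 75% relocated): hazards −ln(0.44)/6 = 0.1368 and −ln(0.25)/6 = 0.2310 per month, hazard ratio 1.69; p1 = 0.5000, p0 = 0.2961, σ1 = 0.6199. n = 61. At 99 patients there are 49.5 events and 94% power by formula (about 93% by simulation).

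Either way the calculation uses the stoma pair alone. The stated 99, 80% and 13 are fully reproduced with no oral-intake rate. That they need the first coding is a separate issue about event direction and is not argued here.

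**What combined power depends on.** This is an illustration under the event-proportion reading, so its starting point is about 93-94%, not 80%. Stoma patients have reference 0.1368 and hazard ratio 1.69. Oral-intake patients have their own assumed reference: median 2 to 12 weeks among those ever released, 53.8-85% ever released, exponential among those released. The oral-intake hazard ratio multiplies the hazard of the whole oral-intake group. Follow-up is 3 months from index use. Z = (ΣO − ΣE)/√ΣE, and superiority is declared if Z > 1.967. There were 20,000 simulated studies per setting.

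| Oral-intake hazard ratio | Combined power, 99 patients | Lowest at | Highest at |
|---|---|---|---|
| 1.0 | 19-46% | 2 weeks, 85% released, 61/38 | 12 weeks, 53.8% released, 50/49 |
| 1.3 | 64-81% | 12 weeks, 53.8%, 61/38 | 2 weeks, 85%, 50/49 |
| 1.69 | 91-99.5% | 12 weeks, 53.8%, 61/38 | 2 weeks, 85%, 61/38 |

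The 53.8% is a stent closure rate from section 3.2, used only to span a range; closure is not release for oral intake.

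**Sensitivity to follow-up.** Section 6.4.5 follows patients for 3 months after discharge, not from index use. Adding 37 days in hospital (the vacuum-therapy average in one small comparison in section 3.2, as an assumption) gives about 4.2 months. The three ranges become about 24-54%, 74-87% and 96-99.7%. The pattern is the same.

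**The case against.** The protocol is candid about the weakness. Section 6.3.7 says that a reasonable calculation is not possible at present, calls the figure initial, prints the stoma assumption in the same sentence as the 80%, and plans a recalculation. The SAP, not at hand, may fix the references. Section 5.2.3 already sets the comparator class, and the plural control groups in section 7, with the stoma cohort only the most prominent source, leave room for event-specific references. All of this stands and limits the point. It does not make the power sentence true for the combined endpoint. The recalculation can change the sample size up to 165 but supplies no null hypothesis for oral intake, and section 7 keeps the test confirmatory.

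Four stronger readings are tempting, and the documents do not support them:

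- *The stoma curve will be applied to oral-intake patients, so false superiority is likely.* Section 7 does not say this, and its wording is compatible with separate references.
- *The study is underpowered.* Combined power may lie below or above 80%, depending on an oral-intake effect that nobody has stated.
- *Counting release for relocation against a reference that counts relocation itself favours the device.* Release comes first, but the documents do not give the reference cohort's time origin, so the net direction is uncertain.
- *The confirmatory claim must be confined to stoma patients.* This would remove at least about half the cohort although sections 5.2 and 5.2.1 set objectives in both tracts. The defect does not require it.

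**Conclusion.** The point holds in a limited form. The 80% power in section 6.3.7 derives from stoma-relocation rates alone and is not a property of the endpoint tested in section 7. At least about half the patients, and about 62% if the 76.4% diversion rate applies, are judged on an event with no stated conventional-care rate, effect size or named reference. The textual part needs no assumption beyond the planned balance of the two tracts.

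The power ranges are illustrations. They rest on the event-proportion reading, proportional hazards within each event type, and assumed oral-intake times and release rates. They show that the answer turns on an unstated quantity; they do not estimate this study's power. The difference between release for relocation and relocation itself is a limitation of unknown net direction in the stoma stratum. The matter should be corrected, but it does not invalidate the design.

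**What to change.** 1. **Section 6.3.7:** state that the 80% rests on the stoma-relocation assumption only and is not established for the combined endpoint.
2. **Section 7:** state that expected events are computed from an event-specific conventional-care reference, one for release for oral intake and one for stoma relocation, with sources fixed before the interim analysis. State that O − E and E are summed over strata in the one confirmatory test, and that each stratum is also reported. In simulations with event-specific references, one-sided type I error was 2.8-3.4% against a nominal 2.46%, so the stratified test stays close to its level.
3. **Limitations (section 6.4.8):** note that the study counts release for relocation while the reference counts relocation, with uncertain net direction.

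The cost is protocol and SAP wording plus a literature search for a conventional-care oral-intake reference. No change to enrolment, follow-up or patient care is needed. Fixing the sources before the interim analysis matters because a reference chosen after seeing interim data would weaken a confirmatory claim in a single-arm study.

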6.4.5 Follow-up (FU) visits

Every patient will be followed for 3 months after discharge after index treatment.

In line with routine clinical care, at least one personal follow up visit should take place within 3 months of follow up. To ensure comparability of data, in case this follow up visit has not been performed after 3 months (± 2 weeks) in addition a phone call with the patient should provide final information to be documented in the FU visit (phone) of the e-CRF.

At the FU visits the following data from clinical routine will be documented in the e-CRF (if available):

- Patient status
- Relevant concomitant medication and other treatment
- Safety related events: SAEs (including SADEs), AEs of special interest (including ADEs) and DD

Assessments*	Baseline visit	Index-Treatment	FU visits
Informed consent for data use	Х		
In- and Exclusion criteria	Х		
Demographic data	Х		
Medical history	Х		
Patient's status	Х		X**
Medication/other treatment	Х	X	X**
Concomitant diseases	Х		
Data regarding index treatment and related therapy		X	
Outcome of index treatment		X	
Safety related events (SAEs, SADEs, ADEs, DD)		X	Х

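### Protocol 6.3.7: 99 patients, 13 events and 80% power do not follow from 75% versus 56% relocated at 6 months; they match those proportions read as event-free

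*Protocol*

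**What the plan says.** Section 6.3.7 of the protocol bases its initial sample size on a published cohort with median times to stoma relocation of "4 months in the EVAC group (interquartile range 3 to 6 months) versus 4 months (3 to 13 months) in the conventional management group". From the upper quartile it concludes that "the proportion of patients with stoma relocation after 6 months is known as 75% in the EVAC group", and by linear interpolation it puts the conventional group at 56%. Both are proportions in whom relocation has happened, and the power statement in the same section uses them in that sense again.

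On the method it says "Sample size calculation was performed with PASS 16.0.3 using a two-sided, one-sample log rank test". The group sequential design "results in a two-sided type one error of 4.92% for the final analysis", and survival times are taken as Weibull with shape 1.00, that is, exponential. On the horizon it says "Even if the follow-up is set to 3 months in this study, sample size calculation can be based on 6 months results".

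The results stated are "A sample size of 99 analysable subjects achieves 80% power to detect shorter time to release for food intake" (or endoscopic release for stoma relocation) and "The expected number of events during the study with 3 months of follow-up is 13". A 10% allowance takes 99 to 110 enrolled, and the cap after recalculation is 1.5 times the initial size, 165.

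Section 6.1.3.1 makes release for oral food intake, or endoscopic release for stoma relocation, the event, with time counted from index use of the device. Section 7 says that superiority over conventional management will be tested confirmatorily.

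**The concern.** A curve that reaches 75% with the event at 6 months under a constant hazard cannot have only 13 of 99 patients with the event at 3 months; half should have had it. The stated event count therefore contradicts the stated inputs before any power formula is chosen.

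The figure of 13 is close to what follows if 75% is the proportion still without the event. If the two proportions were entered that way round, n and power belong to an effect in the opposite direction, slower release on EVAC, and not to the hypothesis the study will test.

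The 110 enrolled and the cap of 165 both rest on the 99. The interim recalculation could repeat the same input orientation, and anyone planning from 13 expected events would find the observed count several times higher.

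**Working it through.** **Inputs (section 6.3.7).** Event proportions at 6 months 0.75 (EVAC) and 0.56 (control); exponential survival; 3 months of follow-up; two-sided alpha 0.0492 (z = 1.967); power 80% (z = 0.842). Fixed 3-month follow-up for every patient and no accrual term are my assumptions.

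**Formula.** One-sample log-rank, with monthly hazards λ1 (EVAC) and λ0 (control) and t = 3:

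- p1 = 1 - exp(-λ1 t), the event probability under the alternative
- p0 = (λ0/λ1) p1, the expected control cumulative hazard under the alternative
- v = p1 + (2λ0²/λ1 - 2λ0) m - (p1 - p0)², with m = p1/λ1 - t exp(-λ1 t), the per-patient variance of observed minus expected
- n = [1.967 √s0 + 0.842 √v]² / (p1 - p0)², with s0 = p0 (null variance) or s0 = (p0 + p1)/2 (averaged variance)

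**Step 1: reproduce the stated figures.** Enter 0.75 and 0.56 as event-free.

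- λ1 = -ln(0.75)/6 = 0.0479; λ0 = -ln(0.56)/6 = 0.0966; hazard ratio 0.496
- p1 = 1 - 0.75^0.5 = 0.134; p0 = 0.270; v = 0.154
- Null variance: n = (1.022 + 0.330)² / 0.136² = 98.8, so 99
- Events at 99: 99 x 0.134 = 13.3; power at 99: 80.1%

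All three published figures match. The averaged-variance form gives n = 79.7, so of these two forms only the null form returns 99. A hazard ratio below 1 for a favourable event means later release on EVAC; in simulation of this case every rejection was in the slower direction.

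**Step 2: the inputs as worded.** Event-free 0.25 and 0.44.

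- λ1 = -ln(0.25)/6 = 0.231; λ0 = -ln(0.44)/6 = 0.137; hazard ratio 1.69
- p1 = 1 - 0.25^0.5 = 0.500; p0 = 0.296; v = 0.384

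| | Stated | As worded, null variance | As worded, averaged variance |
|---|---|---|---|
| n for 80% power | 99 | 61.0 | 74.7 |
| Events at n = 99 | 13 | 49.5 | 49.5 |
| Power at n = 99 | 80% | 93.9% | 89.8% |

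Simulation at n = 99 gave 93% and 91% for the two forms. Other alphas, 6-month follow-up, 24-month accrual and a control proportion of 55.56% were also tried; none brought the as-worded reading near 99 patients or 13 events.

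**Step 3: when would 13 events occur?** As worded, 6 x ln(1 - 13/99)/ln(0.25) = 0.61 months.

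**Step 4: does longer observation explain 13?** Section 6.4.5 says "Every patient will be followed for 3 months after discharge after index treatment", whereas the endpoint clock starts at index use, so actual observation exceeds 3 months. At 4 months the as-worded count is 99 x (1 - 0.25^(4/6)) = 59.7, further from 13.

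**Step 5: does dropping the exponential model explain 13?** The quoted EVAC lower quartile of 3 months gives 0.25 x 99, about 25 events by 3 months. That is not 13 either.

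**Step 6: is the corrected power reassuring?** The exponential model puts 1 - 0.25^0.5 = 50% (EVAC) and 1 - 0.44^0.5 = 34% (control) released by 3 months. The quoted quartiles put 25% in both groups at 3 months and 50% in both at 4 months. With piecewise-constant hazards through those quartiles (an assumption), 99 patients give:

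| Follow-up | Events | Power |
|---|---|---|
| 3 months | about 25 | about 5%, equal to alpha |
| 4 months | about 50 | about 5% |
| 6 months | about 74 | 71 to 76% |

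**The case against.** The strongest reply is that the slip does little harm. The test and alpha levels are untouched, and under the protocol's own model 99 patients are more than enough. Section 6.3.7 also says that a reasonable calculation is not yet possible, calls this one initial, and plans a recalculation that may draw on an external trial. This is fair as far as it goes: the error does not leave the study underpowered under its stated model, and that the recalculation would repeat it is a risk, not a certainty. But the initial figure still fixes 110 and the cap of 165, and the statement is wrong as printed.

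Second, the software output is not shown, and even with the proportions swapped 99 returns only under the null-variance form. That stands: the swap is the likely explanation, inferred from three figures matching together. The conflict between 13 events and 75% at 6 months does not depend on it.

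Third, it can be said that printing 90 to 94% power is odd when the quoted quartiles point to almost none at 3 months, and that the piecewise calculation rests on quartiles in whole months from a source not at hand. Both points stand as limits. The corrected power is conditional on the exponential model, and the piecewise figures are illustrative. They are a reason not to cut enrolment; the arithmetic finding does not need them.

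**Conclusion.** The concern holds and the section must be corrected. With the inputs as worded, exponential survival and 3 months of follow-up, 99 patients give 49.5 events and not 13, a factor of 3.7. Power at 99 is about 90 to 94% and not 80%, and 80% power needs about 61 to 75 patients and not 99. The published triple corresponds to a hazard ratio of 0.50, the wrong direction for the hypothesis.

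The event count rests only on the stated proportions, shape and horizon. The power and n ranges also depend on the variance form and on a fixed 3-month horizon without accrual. None of this is a ground for fewer patients, because the favourable corrected power comes from an exponential curve that the protocol's own quartiles do not support within 3 months.

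**What to change.** In Protocol section 6.3.7:

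- Re-run the one-sample log-rank calculation with event-free proportions of 44% (control) and 25% (EVAC), and name the variance form.
- Keep 110 enrolled and 99 analysable. Restate expected events (about 50) and power (about 90 to 94%) as conditional on the exponential assumption, and say that 99 is retained and is no longer the output of an 80% target.
- State that the quoted quartiles show no separation between groups up to 4 months, and justify the effect assumed within the 3-month horizon.
- State the time origin of the 3 months used in the calculation, given that follow-up in section 6.4.5 runs from discharge and the endpoint from index use.
- Use the correctly oriented inputs in the interim sample-size recalculation.

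The cost is one re-run and a text amendment. It needs no additional patients and no change to the test or the alpha levels.
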